### 2. Introduction

Hypermobile Ehlers-Danlos Syndrome (hEDS) and Hypermobility Spectrum Disorder (HSD) are conditions characterized by abnormal collagen, resulting in many tissues in the body being overly flexible. Joint hypermobility is most obvious, hence the former name for this condition: joint hypermobility syndrome. HSD and hEDS comprise a continuum in which diagnostic criteria for hEDS are narrower. However, the pain and other symptoms such as sleep disturbance, fatigue, anxiety, proprioceptive (body position awareness) deficits, autonomic nervous system dysfunction, GI distress, can exist equally for both conditions.(Tinkle, 2017) The current study seeks to involve people throughout the continuum, hence hEDS/HSD.

Individuals with hEDS/HSD often have movement disorders, such as balance issues, due in part to reduced proprioception (Smith 2013), fear of movement or kinesiophobia and a reluctance to move due to the presence of chronic pain. Pain is often one of the first symptoms to appear with hypermobility (Smith 2013). Other issues such as fatigue and autonomic disorders such as Postural Orthostatic Tachycardia Syndrome (POTS) are also common in hEDS/HSD; these comorbidities can decrease desire to exercise as well as tolerance to upright (standing) exercise. Therapeutic exercise is considered one of the most effective treatment options in the improvement of pain and disability in hEDS/HSD, but optimal type, frequency and intensity are not known.(Smith, 2014; Engelbert, 2017) However, pain, fatigue and fear are common barriers to exercise among people with hEDS/HSD.(Simmonds, 2017) Mind-body exercises, such as Pilates, Tai Chi, and yoga have been recommended for people with hEDS/HSD based on the

fact that these mind-body activities are typically gentle and foster relaxation and improved body awareness.(McNeill, 2018; Russek, 2018)

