Our primary outcome measures will be a hypermobility-specific functional/disability measure, The Bristol Impact of Hypermobility (BloH) questionnaire.(Palmer, 2017) The BloH is a 55 item questionnaire that asks about pain, fatigue, joint instability, function, self-efficacy and attitudes about having hypermobility. It is the only outcome measure specifically validated for hypermobility-related conditions, and it is recommended by the international Common Data Elements initiative, whose goal is to encourage EDS researchers to use consistent outcome measures.

We will also measure physical activity, to determine whether participation in Pilates allows people to become more active. The International Physical Activity Questionnaire Short Form is a validated survey assessing physical activity during work, sport, and leisure time. (Booth, 2000) We will add questions that will track participation in mind-body exercise, such as Pilates, yoga, Tai Chi, etc. and strengthening, as these activities are not included in the IPAQ.

Kinesiophobia will be assessed through the Tampa Scale of Kinesiophobia, short form (TSK-11), which is an 11-question survey asking about fear of movement and fear of injury. (Woby, 2005) The Tampa Scale of Kinesiophobia is one of the recommended Common Data Elements for EDS. We will also collect qualitative data from weekly electronic contact.

The Revised Body Awareness Rating Questionnaire (R-BARQ) includes 12 questions that ask about body awareness, response to discomfort, breathing patters, and physical response to stress.(Dragesund, 2018) This tool may provide insight into the mechanism by which functional improvements are achieved, by correlating functional improvements with improved body awareness, relaxation, effective breathing, etc.

We will also solicit qualitative feedback about the Pilates program through weekly emails. This qualitative information will build upon a recent study using qualitative methods to assess

attitudes towards exercise among people with hEDS/HSD.(Simmonds, 2017)

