The current study will repeat the questionnaires at the end of the 8 week intervention, to assess change, and again 6 months later to determine whether any changes have been maintained. We will also monitor whether subjects continue to do the Pilates exercises at 6 months, either using the videos or on their own. If findings in the current study are encouraging, a more formal randomized control trial would be an appropriate progression. The qualitative data may provide useful information about how to implement a follow-up study more effectively.

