# 3. Objectives and Hypotheses

- 1. Implement a pilot study to assess whether this on-line Pilates course for people with hEDS/HSD results in beneficial changes when compared to a wait-list comparison group. We understand that the evidence will not be strong with a non-random comparison group, but having a comparison group is better than not having one. We hypothesize that 8 weeks of this specialized Pilates training will result in:
  - a. Decreased pain and symptoms, improved function and quality of life (measured using the BloH),
  - b. Increased physical activity (measured using IPAQ with additional questions)
  - c. Improved body awareness (R-BARQ) and less dysfunctional breathing patterns (R-BARQ)
  - d. Decreased fear of movement (TSK-11).
- 2. Pilot test the proposed outcome measurement tools for such a future study. We are looking for basement and ceiling effects, as well as change over time.
- 3. Explore whether certain patterns of implementation of the on-line course are associated with better outcomes. For example, is it better to repeat one module multiple times before moving on, or to move around among modules? This will be descriptive correlational data.
- 4. Gather qualitative data to better understand factors that may influence compliance or maximal benefit. These data can inform future research into either Pilates or use of internet-accessible exercise training for this population. This qualitative information also provides insights into factors that influence participation in exercise within this population, and whether certain patterns are observed among people who benefit from the program compared to those who do not.

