### e. Analysis of outcomes:

- Quantitative data will be coded and entered into Excel, reviewed for outliers, and transferred to SPSS
- Descriptive statistics related to demographics and initial scores for BIoH, IPAQ, TSK-11, R-BARQ
- Descriptive statistics related to subjects use of the different modules (which Pilates modules were used during each of the 8 weeks and overall), and continued use of the modules through the 6 month follow-up.

- Repeated Measures ANOVA comparing pretest, post-test (8 wk) and 6 month after post-test: BIOH, IPAQ, TSK-11, R-BARQ
- ANOVA comparing change over 8 weeks for the Pilates group vs. the wait-list group: BloH, IPAQ, TSK-11, R-BARQ
- Regression analysis using IPAQ, TSK-11, R-BARQ to predict quality of life and function as measured using BloH before intervention, after intervention (including compliance) and 6 months later (including compliance).
- Qualitative analysis of the narrative (email) information using content analysis using the following process:(Bengtsson, 2016)
  - o Decontextualization to identify meaning units, create code list
  - o Recontextualization to verify that all important information has been coded
  - o Categorization to organize themes, with triangulation by investigators
  - Compilation to formulate conclusions, audit, member check if subjects agree

We understand that the lack of a randomized control group makes our current design less rigorous than a randomized control trial (RCT), but having a wait-list comparison group makes the design stronger.

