# c. Address how subjects will be monitored for adverse effects and what remediation is offered.

The research will include a weekly email to touch base with each subject, reminding them to participate at the level they are comfortable (doing any, all, or no Pilates). Subjects will be asked about increased pain or problems, beyond mild soreness from doing new exercises, that they think may be due to the Pilates exercises, as that is important data. Subjects will be reminded: "If you have increased pain or problems, either due to the Pilates exercises or any other reason, please modify or omit any or all Pilates exercises that do not feel safe to do and contact your health care provider as appropriate." However, no remediation will be offered or provided.

Subjects

- d. Does the data to be collected relate to illegal activities? If so explain. NA
- **e.** Rate risk level. Check the most appropriate risk level below. (Minimal risk means that the probability and magnitude of harm or discomfort anticipated in the research are not greater in and of themselves than those ordinarily encountered in daily life or during the performance of routine physical or psychological examinations or tests.)

The research involves no more than minimal risk to subjects.
The research involves more than minimal risk to subjects but the risk(s) represents a minor increase
over minimal risk, or
The research involves more than minimal risk to subjects and the risk(s) represents more than a minor
increase over minimal risk

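### The 8-week and 6-month regressions omit baseline BIoH, so the compliance coefficient shows who is less affected at that time and can reflect who was milder at the start

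*Combined protocol and SAP*

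**What the plan says.** Section 6e (Analysis of outcomes) describes one regression fitted at three times: "Regression analysis using IPAQ, TSK-11, R-BARQ to predict quality of life and function as measured using BloH before intervention, after intervention (including compliance"), and once more at 6 months, again with compliance. Compliance is the only term added after the intervention. Baseline BIoH is not listed, nor is a BIoH change score. The text does not say whether the three scales enter as baseline or concurrent values.

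Change is analysed elsewhere in section 6e, by a repeated measures ANOVA over three times and an ANOVA of 8-week change between the Pilates and wait-list groups. Neither lists compliance. Module use by week and overall is to be summarised descriptively.

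The aims are worded in terms of improvement. The Introduction (section 2) hopes to learn about mechanism "by correlating functional improvements with improved body awareness, relaxation, effective breathing, etc". Objective 3 (section 3) is to "Explore whether certain patterns of implementation of the on-line course are associated with better outcomes", and adds: "This will be descriptive correlational data".

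**The concern.** A model of BIoH level at follow-up answers a different question from a model of improvement. Someone mildly affected at the start will usually still be mildly affected at 8 weeks, whatever the course did.

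That matters for compliance because it is not assigned. The weekly contact is described in section 7c as "reminding them to participate at the level they are comfortable (doing any, all, or no Pilates"), and Appendix H tells subjects they remain in the study however much Pilates they do. The Introduction states that "pain, fatigue and fear are common barriers to exercise among people with hEDS/HSD", and question 3 of the weekly survey offers pain and fatigue among the reasons for doing less. BIoH itself "asks about pain, fatigue, joint instability, function, self-efficacy and attitudes about having hypermobility". Baseline severity may therefore influence both how much a person uses the course and the follow-up score, and it is left out of the model.

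At stake is what the pilot passes on. Objectives 3 and 4 look for patterns of use and factors behind benefit to inform later research. A compliance coefficient that mixes being milder at the start with changing alongside use is a weak guide for that, even when read as description.

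**Working it through.** **No figure to reproduce.** The documents give no correlation, SD, alpha or power for these regressions. What follows illustrates the mechanism under assumed values.

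**Inputs.** From the documents: n = 225, the number recruited before the wait-list begins (section 6a), taken with no dropout. Assumed: no true effect of use; all variables standardised; pre-post BIoH correlation ρ = 0.75; each scale correlated k = 0.45 with BIoH, and the scales independent of everything else given BIoH; compliance correlated r with baseline BIoH; a two-sided 0.05 threshold.

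**Step 1: what the three scales capture.** Their joint R² with BIoH is q = 3k²/(1+2k²) = 0.6075/1.405 = 0.4324.

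**Step 2: compliance coefficient as planned, r = -0.2.**
- Baseline scales: b = ρr(1-q)/(1-r²q) = 0.75 × (-0.2) × 0.5676/(1-0.04×0.4324) = -0.0851/0.9827 = -0.087.
- Concurrent scales: b = ρr(1-q)/(1-ρ²r²q) = -0.0851/0.9903 = -0.086.

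**Step 3: how often |z| exceeds 1.96.** The residual df are 225-5 = 220.
- Baseline scales: R² = ρ²(r²+q-2r²q)/(1-r²q) = 0.2506. SE = √(0.7494/(0.9827×220)) = 0.0589, z = -1.47, rate about 31%.
- Concurrent scales: with c = ρr = -0.15, R² = (c²+q-2c²q)/(1-c²q) = 0.4397. SE = √(0.5603/(0.9903×220)) = 0.0507, z = -1.70, rate about 40%.

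Simulation with 5,000 studies per setting agrees:

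| r | Planned, concurrent scales | Planned, baseline scales | Either, plus baseline BIoH |
|---|---|---|---|
| 0 | 5% | 5% | about 5% |
| -0.1 | 14% | 11% | about 5% |
| -0.2 | 40% | 31% | about 5% |
| -0.3 | 72% | 61% | about 5% |

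With baseline BIoH in the model the mean coefficient is 0.

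**Step 4: sensitivity at r = -0.2.**
- k from 0.6 down to 0.3: the coefficient runs from about -0.06 to -0.12; rates are 28% to 50% (concurrent) and 18% to 47% (baseline). With n = 150 (assumed dropout) they are 21% to 37% and 13% to 32%.
- ρ of 0.6 and 0.85: 28% and 49% (concurrent), 21% and 43% (baseline).
- r = +0.2: rates of 39% and 31%, but compliance then looks harmful (about +0.09).

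**Step 5: what baseline adjustment leaves behind.** Suppose compliance follows average health over the 8 weeks, with correlation -0.2 to the mean of pre and post BIoH. Its correlation with each BIoH score is c = -0.2×1.75/√3.5 = -0.187. Adjusted for baseline BIoH, b = c(1-ρ)/(1-c²) = -0.0468/0.965 = -0.048. Baseline scales add nothing here, being independent given baseline BIoH. The residual variance is 0.435, SE = √(0.435/(0.965×219)) = 0.045 and z = -1.07, so the rate is about 19%. The planned model gives 57% to 59%.

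**Step 6: why the baseline scales should stay.** Let compliance correlate -0.3 with baseline TSK-11, and let TSK-11 carry a further effect d on follow-up BIoH. With only baseline BIoH and compliance in the model, b = -0.3×(1-0.2025)d/(1-0.135²) = -0.244d. For d = 0.1 and 0.2 that is -0.024 and -0.049. With SE about 0.045 the rates are about 8% and 19%. With the baseline scales kept, the rate is 5%.

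**The case against.** The strongest reply is that nothing here is an error. Section 6e says only that the scales predict BIoH, Objective 3 calls the usage work descriptive, and section 6e states no alpha and no test of an effect of use. In the illustration, compliance really is associated with follow-up BIoH given the scales, so a descriptive model that finds it is right. This stands: the percentages must not be read as type I error rates of a planned test. They show how often an association would appear with no effect of use behind it.

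A second reply is that IPAQ, TSK-11 and R-BARQ already stand in for severity. They do so in part, and the rates above include all three. TSK-11 also measures the fear that the Introduction names as a barrier, which is why step 6 keeps it.

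A third is that the weekly survey asks about symptoms during the programme rather than at baseline. That is fair, and step 5 shows that baseline adjustment reduces this confounding without removing it.

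A reader might infer that the trial's main comparisons are compromised. The documents do not support that: both ANOVAs are separate analyses without a compliance term. The Introduction's remark that, after encouraging findings, "a more formal randomized control trial would be an appropriate progression" follows its account of repeated questionnaires, so it rests at least as naturally on those ANOVAs. A reader might also infer that compliance will be flattered. No correlation is given, and more affected people might use the course more. Nor does the plan ignore module use: it is described by week, and only its link to outcome is missing.

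**Conclusion.** The point holds for the two follow-up regressions. They omit baseline BIoH, so their compliance coefficient describes status at that time and can reflect status at the start. No planned model relates compliance to change in BIoH, which leaves a gap between section 6e and the aims in sections 2 and 3.

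Confounding by baseline severity is plausible on the documents' own account of barriers and self-chosen use. Its size and sign cannot be derived from them. Under the assumed correlations at r = -0.2, the coefficient is about -0.06 to -0.12 SD of BIoH per SD of compliance with no effect of use, and there is no distortion if compliance is unrelated to baseline BIoH. The pre-intervention regression is cross-sectional and unaffected. The change is worth making because it is nearly free, but it concerns exploratory associations only.

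**What to change.** In section 6e:

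- At 8 weeks and at 6 months, regress follow-up BIoH on baseline BIoH, the baseline values of IPAQ, TSK-11 and R-BARQ, and compliance from the module log. State how logged access is counted, since section 6a lets subjects pause a session and finish later.
- Keep concurrent and change scores of the scales out of this model, because they may be mediators of any benefit.
- For wait-list subjects, who answer the surveys twice before Pilates, take the survey completed immediately before they start as baseline.
- If the mechanism question in the Introduction is to be answered, fit a separate model of follow-up BIoH on baseline BIoH and change in R-BARQ.
- Keep the pre-intervention regression as a cross-sectional description, and report all coefficients as exploratory associations.

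The cost is a few sentences and one extra covariate per model, plus the optional mechanism model. The scores and the module log are already collected. Confounding by symptoms during the 8 weeks remains and should be acknowledged in the report.

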### 7. Risks and Benefits

a. Risks: detail stress, physical, psychological, social or economic harm that may be incurred by participation in this research? Describe risks (including risks associated with release of personal information) and methods for minimizing these risks.

Pilates is extremely gentle and intended to reduce pain; it is therefore unlikely that subjects will experience any pain or injury from participating in the activity. While, some soreness is always a possibility after beginning a new exercise/activity, 80 people have previously subscribed to this online Pilates course and none have reported any adverse effects. A systematic review of Pilates for low back pain found only 2 studies that discussed adverse events: one study reported no events and the other study reported 2 minor events.(Yamato, 2016) Furthermore, participation in this research creates no greater risk than if people signed up for this program outside of this research. Risk of harm is minimized by emphasizing self-awareness and safety during classes, and instructing subjects to omit any exercise in the videos that causes discomfort or does not feel safe to them. The disclaimer applied to all of [name]'s on-line Pilates classes has been added to the informed consent so that the knowledge of possible risks and responses is the same for our research participants as for anyone signing up for one of her on-line courses.

There is minimal risk of private information being revealed, as subjects will use an ID code known only to them for their data on SurveyMonkey. Thus, all of the survey data will be collected, stored and analyzed without any personal identifiers. Access to the Pilates course will be tracked using subjects' email address and their self-generated research code; only [name] will know subjects' email address, but she will not have access to personal information shared on SurveyMonkey. Reminder emails will be sent out by [name] using subjects' email address, but these emails will link to SurveyMonkey where subjects can enter their self-generated research ID. Subjects will not email any information to [name] as part of the research (though they are allowed to contact her independently with questions about the exercises, as are all users of her programs). [name] and [name] will have access to the SurveyMonkey data, but will not have email addresses. Since subjects will receive access to the Pilates course free of charge, subjects will not be providing credit card information.

We will be asking for qualitative information in the weekly check-in. Although we will explicitly ask subjects to not include any identifiable information in these narrative responses, it is possible that they might. Any identifiable information will be deleted when narrative data are extracted from SurveyMonkey for further data analysis.

b. For subjects in the EU, Iceland, Liechtenstein, and/or Norway, describe how you will comply with GDPR regulations. For additional information about the GDPR, please see https://rgs.usu.edu/irb/wp-content/uploads/sites/12/2018/04/GDPR-Guidance.pdf. According to GDPR regulations, we will be collecting Personal Data as we will be using subjects' email address to contact them, send them links to surveys, and enroll them in the Pilates course. All data entered into SurveyMonkey (all data except utilization of the on-line modules) will be through a subject-generated identification code, so the data in SurveyMonkey will be anonymous. [name], who runs the on-line Pilates courses, will have email addresses and the subject-generated ID

code so that we can track compliance, but she will not have direct access to the remaining data. All data will be stored using the subject-generated ID code. Once data collection for any individual is complete, that person's email address will be deleted from the research data, which will then be anonymous. [name] will continue to have access to the email address as long as that individual wants to continue accessing the Pilates modules.

# c. Address how subjects will be monitored for adverse effects and what remediation is offered.

The research will include a weekly email to touch base with each subject, reminding them to participate at the level they are comfortable (doing any, all, or no Pilates). Subjects will be asked about increased pain or problems, beyond mild soreness from doing new exercises, that they think may be due to the Pilates exercises, as that is important data. Subjects will be reminded: "If you have increased pain or problems, either due to the Pilates exercises or any other reason, please modify or omit any or all Pilates exercises that do not feel safe to do and contact your health care provider as appropriate." However, no remediation will be offered or provided.

Subjects

- d. Does the data to be collected relate to illegal activities? If so explain. NA
- **e.** Rate risk level. Check the most appropriate risk level below. (Minimal risk means that the probability and magnitude of harm or discomfort anticipated in the research are not greater in and of themselves than those ordinarily encountered in daily life or during the performance of routine physical or psychological examinations or tests.)

The research involves no more than minimal risk to subjects.
The research involves more than minimal risk to subjects but the risk(s) represents a minor increase
over minimal risk, or
The research involves more than minimal risk to subjects and the risk(s) represents more than a minor
increase over minimal risk

